Sonothrombolysis in Patients with an ST-segment Elevation Myocardial Infarction

A prospective single-arm study

Author(s): [name] and [name]

Protocol # ST2017-Pro00067953

NCT# 03092089

Version (3): 13-Feb-2017

Study Coordinating Group: ABACUS

Mazankowski Alberta Heart Institute

University of Alberta Edmonton, Canada

[name]

STUDY SYNOPSIS

Title	Sonothrombolysis in Patients with ST-segment Elevation Myocardial Infarction (STEMI)	
Investigator(s)/center/study location	Investigator-initiated prospective, single-center, single- arm study	
Study Objectives	To assess the efficacy and safety of sonothrombolysis in the acute management of STEMI undergoing reperfusion therapy with primary percutaneous coronary intervention [PPCI].	
Study Design	The sonothrombolysis in STEMI study will be an investigator-initiated prospective, single center, single-arm study of sonothrombolysis performed before coronary reperfusion with PPCI.	
Study population Inclusion criteria:	Patients presenting with STEMI within 6 hours of symptom onset and: 1. Are expected to receive reperfusion therapy with primary PCI 2. Have a high-risk STEMI ECG defined as: • ≥2mm ST-segment elevation in 2 anterior or lateral leads; or • ≥2 mm ST-segment elevation in 2 inferior leads coupled with ST-segment depression in 2 contiguous anterior leads for a total ST-segment deviation of ≥4 mm 3. Age ≥30 years. 4. Adequate apical and/or parasternal images by echocardiography.	
Exclusion criteria:	 Isolated inferior STEMI without anterior ST-segment depression Previous coronary bypass surgery 	

[figure not shown]
	 Cardiogenic shock Known or suspected hypersensitivity to ultrasound contrast agent used for the study Life expectancy of less than two months or terminally ill. Known bleeding diathesis or contraindication to glycoprotein 2b/3a inhibitors, anticoagulants, or aspirin Known large right to left intracardiac shunts.
Evaluation criteria	Primary Outcome 1. Spontaneous reperfusion as assessed by a pre PCI ECG complete ST-segment resolution (>50%) (immediately prior to angiogram) and by pre PCI TIMI 2-3 flow on diagnostic angiogram.
	 Complete (>50%) ST-segment resolution at 30 minutes post PCI as assessed by the worst lead on electrocardiogram (ECG core lab). Left ventricular ejection fraction (LVEF) by echocardiography (ECHO) (Simpson method) assessed on day 1 (pre and post reperfusion), day 3±2 (discharge) and 90±2 days after infarction. Wall motion score index (WMSI) by ECHO assessed on day 1 (pre and post reperfusion), day 3±2 (discharge) and 90±2 days after infarction. Microvascular perfusion score index (MPSI) by ECHO assessed on day 1 (pre and post reperfusion), day 3±2 (discharge) and 90±2 days after infarction.
Treatment	Sonothrombolysis: Echocardiographic imaging with intermittent diagnostic high mechanical index (MI) using a commercially available echocardiography scanner (Epiq,Philips Healthcare) to the myocardium during an intravenous 5% Definity infusion (Lantheus Medical) over a maximum 30 minute treatment period (started prior to PCI)

Statistical Considerations	Efficacy Analysis : This is an observational study to reproduce findings of a previous study which showed angiographic spontaneous reperfusion rates of 80% with sonothrombolysis prior to PCI (i.e. pre PCI TIMI 2-3 flow). If we can demonstrate a patency rate > 60%, a multicenter study will be arranged.
Sample Size	15 patients
Duration of Follow-Up	Minimum of 90 +/- 7 days

1.0 OVERVIEW OF STUDY DESIGN

Patients presenting with ST-segment elevation myocardial infarction undergoing reperfusion therapy (fibrinolysis or primary PCI)

All patients receive ASA and other standard therapies

IN-HOSPITAL AND 90-DAY FOLLOW-UP

Primary Outcome

1. Spontaneous reperfusion as assessed by a pre PCI ECG complete ST-segment resolution (>50%) (immediately prior to angiogram) and by pre PCI TIMI 2-3 flow on diagnostic angiogram..

Secondary Outcomes

- 1. Complete (>50%) ST-segment resolution at 30 minutes post PCI as assessed by the worst lead on electrocardiogram (ECG core lab).
- 2. Left ventricular ejection fraction (LVEF) by echocardiography (ECHO) (Simpson method) assessed on day 1 (pre and post reperfusion), day 3±2 (discharge) and 90±2 days after infarction.
- 3. Wall motion score index (WMSI) by ECHO assessed on day 1 (pre and post reperfusion), day 3±2 (discharge) and 90±2 days after infarction.
- 4. Microvascular perfusion score index (MPSI) by ECHO assessed on day 1 (pre and post reperfusion), day 3±2 (discharge) and 90±2 days after infarction.

2.0 INTRODUCTION AND RATIONALE

In Canada, more than 40,000 patients are hospitalized with an acute coronary syndrome (ACS) each year of which one-third suffer an ST-segment elevation myocardial infarction (STEMI) (1,2). As such, STEMI remains a significant public health concern given the substantial morbidity and mortality associated with the condition (3-7). Prompt reperfusion therapy has been shown to reduce mortality, infarct size and improve left ventricular function (8-13).

However, it has been recognized that reperfusion itself may result in adverse events. Abrupt reperfusion therapy can lead to myocardial stunning, ventricular arrhythmias and microvascular dysfunction as a result of distal coronary embolization and myocardial inflammation. This injury pattern inflicted upon the myocardium has been termed reperfusion injury (14). The accumulating effects result in myocyte necrosis, myocardial stunning and impaired infarct healing contributing to microvascular dysfunction and subsequent adverse clinical events in STEMI (15-19). The bedside electrocardiogram is a simple non-invasive tool that can be used to assess microvascular perfusion as defined by the degree of ST-segment resolution following the administration of reperfusion therapy (20).

Multiple mechanisms to reduce infarct size have been undertaken with limited success and inconsistent results(21). While transthoracic high mechanical index (MI) impulses from a diagnostic ultrasound (DUS) transducer have been utilized to diagnose microvascular obstruction and detect myocardial perfusion during a continuous microbubble infusion(22-26), the microbubble cavitation induced by these high MI impulses(27) creates shear forces that are capable of dissolving epicardial and microvascular thrombi in animal models of acute STEMI (28-30). These same high MI impulses, when applied to the microvasculature, also induce nitric oxide release (31), which may further augment microvascular flow. Termed sonothrombolysis, these effects have been demonstrated and verified in animal models, however the utility of DUS in humans has not been well studied during the contemporary management of STEMI, where emergent reperfusion (primary percutaneous coronary intervention [PPCI] or fibrinolysis) is routinely employed with such rapidity that only brief applications of ultrasound may be possible prior to interventional therapies. Recently in a small PPCI STEMI randomized trial (N=20 treated with sonothrobolysis), high MI with DUS (continuous microbubble infusion) (sonothrombolysis) was associated with improved patency rates of the infarct vessel prior to PCI. Specifically, the infarct related artery was found to be open in 80% with sonothrombolys is compared to patients with standard of care prior to PCI (~20%). If these results can be reproduced with another ultrasound system, a large clinical trial may be warranted (32). No serious adverse events were reported in this study and in a small previous study involving five patients (33). However, in another study vasoconstriction in the culprit coronary artery was observed in three out of six patients during coronary angiography (34). In this study the pulse duration of the ultrasound scanner was prolonged in order to expose the intracoronary thrombus and the ultrasound contrast to a higher power. One patient withdrew from the study and was lost during follow up (but still alive according to the Dutch national registry), the other two patients had no long term side effects. The authors stress the higher ultrasound power used in this trial (20 µs instead of 5 µs which is transmitted in diagnostic ultrasound) and explain the findings by a "summative effect of

Sonothrombolysis in Patients with an ST-segment Elevation Myocardial Infarction Protocol #ST2017-Pro00067953 Version (3): 13-Feb-2017 myocardial ischemia, reperfusion, damage and long-pulse-duration sonoporation on endothelial damage, all leading to calcium overload. It was concluded that new trials should proceed with short (5 μ s) pulse duration. Therefore we will use the pulse duration of 5 μ s which is clinically used for diagnostic ultrasound in the proposed pilot study.

The purpose of this study was to examine what effect adding emergent DUS guided high MI impulses (sonothrrombolysis), applied both before PPCI during an intravenous commercially available microbubble infusion (5% Definity, Lantheus Medical Imaging, Inc., North Billerica, Massachusetts), have on spontaneous reperfusion (i.e. pre PCI coronary artery patency rates), microvascular obstruction, left ventricular function and infarct size in patients presenting with their first STEMI. Accordingly, given the potential impact of utilizing this practical application for attenuating reperfusion injury, we propose a prospective, single center, single-arm study of pre-procedural sonothrombolysis as an adjuvant to contemporary therapy for ST-segment elevation myocardial infarction receiving PPCI.

3.0 STUDY HYPOTHESIS

In adult patients with high-risk ST-segment elevation myocardial infarction (STEMI) planned for reperfusion therapy (primary PCI), the use of sonothrombolys is will enhance spontaneous reperfusion (i.e. pre-PCI ST-resolution and pre-PCI epicardial patency). We expect that >60% of the patients will have an open infarct vessel at the beginning of coronary angiography.

4.0 STUDY OBJECTIVES

4.1. Primary Objective

To determine whether the use of sonothrombolys is along with standard therapy in patients with STEMI undergoing reperfusion therapy (primary PCI) is resulting in a higher rate of spontaneous reperfusion (i.e. pre-PCI ST-resolution and pre-PCI epicardial patency) compared to standard therapy alone.

4.2. Secondary Objective

To determine whether the use of sonothrombolys is along with standard therapy in patients with STEMI undergoing reperfusion therapy (primary PCI) is resulting in better microvascular function than what is reported for standard therapy alone.

4.3. Tertiary Objective

To determine whether the use of sonothrombolysis along with standard therapy in patients with STEMI undergoing reperfusion therapy (primary PCI) is resulting in improved left ventricular function compared to what is reported for standard therapy alone.

5.0 STUDY DESIGN

5.1. Study Design

This clinical study is a prospective single-center, single-arm investigation of sonothrombolys is in adult patients presenting with high-risk STEMI within 6 hours of the onset of clinical symptoms and receiving reperfusion therapy with PPCI. All patients will receive standard therapy according to the current American College of Cardiology / American Heart Association (ACC/AHA) or European Society of Cardiology (ESC) STEMI and PCI guidelines (35).

The Vital Heart Response Program (VHR) facilitates treatment of patients with STEMI within the pre-hospital emergency medical services environment as well as within emergency departments within the Edmonton region via a STEMI network. After completion of initial clinical assessment and documentation of a 12-lead with diagnostic ST-elevation, patients will be approached for participation.

5.2. Intervention (sonothrombolysis)

Patients will immediately receive an intravenous infusion of commercially available ultrasound contrast agent (5% Definity, Lantheus Medical Imaging, Inc., North Billerica, Massachusetts)

1.3 mL diluted in 50 ml saline and infused running at 2 to 5 ml/min. After starting the infusion, myocardial contrast echocardiography will be performed using a commercially available echocardiography scanner (Epiq, Philips) with a diagnostic ultrasound transducer (X5-1) and a preset for myocardial perfusion imaging. 4-, 2- und 3-chamber views will be recorded to document the size of the perfusion defect according to method published by Porter et al (27). The focus will be set at the mitral valve level for all studies. Loops of 15 cardiac cycles will be recorded using low mechanical index (MI) ultrasound with a 'flash' delivered after the second cardiac cycle of the loop. The flash is a short impulse of high MI ultrasound* which is transmitted to destroy the ultrasound contrast in the myocardium and then to assess the replenishment of myocardial contrast. These recordings will also be used to assess regional wall motion as well as the LV volumes and ejection fraction.

* Mechanical index (MI) is the unit to measure the ultrasound energy transmitted by the ultrasound transducer. High MI (>0.8) ultrasound imaging is the standard for echocardiographic imaging without contrast agents. In contrast echocardiography, however, high MI leads to destruction of the microbubbles in the contrast agent. Therefore contrast imaging has to be performed with very low MI (<0.2), fortunately there are very sensitive postprocessing tools that can still detect the specific signals from contrast agent at very low MI. In myocardial perfusion imaging, high MI ultrasound is applied only briefly to clear the myocardium from the contrast agent and to assess the time it takes for the blood from the aorta to reach the microvessels. In diagnostic imaging this is performed several times in multiple imaging planes in order to detect myocardial thickening and to assess myocardial perfusion. In this pilot trial we are using the same techniques. The ultrasound scanning time will be in the range of that of echocardiographic imaging in clinical practice. The total

Sonothrombolysis in Patients with an ST-segment Elevation Myocardial Infarction Protocol #ST2017-Pro00067953 Version (3): 13-Feb-2017 amount of the ultrasound contrast agent Definity® will be similar to what is clinically used in stress echocardiography and not exceed the maximum dose which is approved for clinical use.

Immediately after the diagnostic ultrasound, the therapeutic ultrasound will start using the same transducer by applying multiple high mechanical index (MI) ultrasound impulses (HMI). The HMI are the same as those which are used for assessment of myocardial perfusion in diagnostic ultrasound. These pulses will be applied in the apical 4-, 2-, and 3-chamber views to the apical windows that contained the risk area. The intervals between HMI impulses will vary from 5 to 15 s depending on the time required for myocardial contrast replenishment.

The following measurements will be performed on the recordings obtained before sonothrombolysis, after completion of sonothrombolysis, 72h or prior to hospital discharge and 3 months after sonothrombolysis:

- 1. Wall motion score index (WMSI) will be computed by analyzing wall thickening in all 3 contrast-enhanced apical windows using a 17-segment model as recommended in the 2015 American Society of Echocardiography Recommendations for Chamber Quantification.
- 2. Biplane measurements of LVEF by the the Simpson method
- 3. Microvascular perfusion score index (MPSI) within the same 17-segment model used for assessment of regional wall motion using a scoring system of 1 for myocardial contrast replenishment within 4 s of the applied HMI impulse; a score of 2 (mildly reduced) when complete replenishment within the risk area is delayed longer than 4 s after the HMI impulse; or a score of 3, which was defined as virtually no replenishment of myocardial contrast over 10 s after the MI impulse. The score index will be computed as total score divided by total number of segments analyzed. Attenuated basal segments will not be included in the calculation.
- 4. Global longitudinal strain

Table.1 Diagnostic and therapeutic procedures

Baseline diagnosis of STEMI (pre-reperfusion)		
day 1	12-lead electrocardiogram-baseline	in ER
day 1	Diagnostic Ultrasound - baseline	start in ER or cath lab
		Myocardial Contrast Echo (MCE)
		LV ejection fraction
		WMSI
		Global longitudinal strain
day 1	Sonothrombolys is A	start immediately after MCE
		prior to reperfusion

day 1	12-lead electrocardiogram-immediately prior to PPCI	in cath lab	
Reperfusion (PPCI)			
day 1	Sonothrombolys is B	start immediately after reperfusion to complete a total of 30 min same method as before reperfusion	
day 1	12-lead electrocardiogram-30 min post PCI	in CCU	
day 1	Diagnostic ultrasound – post intervention	Myocardial Contrast Echo LV ejection fraction WMSI Global longitudinal strain	
day3/discharge	Diagnostic ultrasound	Myocardial Contrast Echo LV ejection fraction WMSI Global longitudinal strain	
day3/discharge	12-lead electrocardiogram-discharge	in CCU/Ward	
3 months	Diagnostic ultrasound	Myocardial Contrast Echo LV ejection fraction WMSI Longitudinal strain	

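### The one stated Definity preparation lasts 10.3 to 25.7 min at the permitted rates, which does not fit Table 1's 30-minute total, and the synopsis and Table 1 disagree on whether 30 min is a limit or a requirement

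*Combined protocol and SAP*

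**What the plan says.** Section 5.2 states the preparation and rate once: "1.3 mL diluted in 50 ml saline and infused running at 2 to 5 ml/min". The order of events in the same section is that the infusion starts, then the baseline scan is done ("After starting the infusion, myocardial contrast echocardiography will be performed"), then treatment follows: "Immediately after the diagnostic ultrasound, the therapeutic ultrasound will start using the same transducer".

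Table 1 in section 5.2 splits treatment into session A, before reperfusion, and session B, which is to "start immediately after reperfusion to complete a total of 30 min same method as before reperfusion". It also lists a separate post-intervention contrast echo on day 1.

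The Treatment row of the synopsis describes the impulses as given "during an intravenous 5% Definity infusion (Lantheus Medical) over a maximum 30 minute treatment period (started prior to PCI".

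For the total amount of agent, section 5.2 says that it will resemble clinical use in stress echocardiography and will "not exceed the maximum dose which is approved for clinical use". Neither statement carries a number.

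**The concern.** Volume, rate and duration are tied by simple division, and the three stated values do not agree. A reader following Table 1 would find the preparation empty before the 30 min are complete, at every rate the protocol allows, with no instruction for that moment.

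This matters because section 2.0 attributes the effect to cavitation of microbubbles, so time with contrast running is the dose-like quantity of this intervention. The study is meant to reproduce an earlier result, and a patency rate above 60% leads to a multicentre study. The planners of that study will need to know what exposure lay behind the rate. As written, two patients treated within the protocol could have very different contrast-on times.

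**Working it through.** **Inputs**

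- Agent 1.3 mL, saline 50 mL, rate 2 to 5 mL/min: section 5.2.
- Total treatment time 30 min: Table 1 (as a total to be completed) and synopsis (as a maximum).
- Infusion running during the baseline echo: section 5.2. The length of that echo is not stated.

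**Does the stated preparation give 30 min?**

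Prepared volume = 50 + 1.3 = 51.3 mL. Time covered = volume / rate. Volume for 30 min = 30 × rate. Preparations = that volume / 51.3. Agent = preparations × 1.3 mL.

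| Rate (mL/min) | Time covered (min) | Short of 30 min by (min) | Volume for 30 min (mL) | Preparations | Agent (mL) |
|---|---|---|---|---|---|
| 2 | 25.65 | 4.35 | 60 | 1.17 | 1.52 |
| 3 | 17.10 | 12.90 | 90 | 1.75 | 2.28 |
| 4 | 12.82 | 17.18 | 120 | 2.34 | 3.04 |
| 5 | 10.26 | 19.74 | 150 | 2.92 | 3.80 |

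The 30 min are not reproduced at any permitted rate. The preparation would last that long only at 51.3 / 30 = 1.71 mL/min, below the stated range. Pausing the infusion during PCI does not change this, since 30 min under infusion still takes at least 60 mL.

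**Other readings of the dilution**

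- Made up to 50 mL: 50/2 = 25 min down to 50/5 = 10 min.
- The stated mix is 1.3/51.3 = 2.5%, while the agent is labelled 5% in the synopsis and section 5.2. At 5% keeping 1.3 mL of agent, the volume is 1.3/0.05 = 26 mL, lasting 13 to 5.2 min. At 5% keeping 50 mL of saline, it is 50/0.95 = 52.6 mL, lasting 26.3 to 10.5 min.

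None reaches 30 min.

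**Effect of the baseline echo**

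The echo uses part of the same infusion. Assuming it takes 3 to 10 min (my assumption, not in the documents), what is left for treatment is 25.65 − 3 = 22.65 to 25.65 − 10 = 15.65 min at 2 mL/min, and 10.26 − 3 = 7.26 to 10.26 − 10 = 0.26 min at 5 mL/min.

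**The two readings of 30 min**

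- Table 1 governs: more than one preparation's volume is needed, and no section provides for it.
- Synopsis governs: treatment may stop when the infusion does. One preparation's contrast-on time then ranges over 25.65/10.26 = 2.5-fold, with no rule for choosing the rate, and session B gets whatever is left, possibly nothing.

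**Which outcomes are touched**

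The primary outcome is measured before PCI (section 7.1), so only session A can affect it. It is reached if baseline echo plus session A exceed 25.65 min at 2 mL/min or 10.26 min at 5 mL/min. Neither duration is given. Otherwise the shortfall falls in session B and bears on the post-PCI outcomes of section 7.2.

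**The case against.** The best defence is that the conflict rests on one table cell. The synopsis makes 30 min a ceiling and places the impulses within the infusion, so treatment can end with the contrast and nothing is given without it. A reader might infer that patients must receive either impulses without microbubbles or more than the stated amount. The documents do not support that as a necessity, because it follows only if Table 1 governs. What stands is that the two places differ, and that the synopsis reading leaves session B undefined.

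Second, the wording in section 5.2 may be a recipe to be repeated as needed, not the day's total. The separate clause on total amount points that way, and so does Table 1's instruction that session B use the same technique as session A. Contrast echo at discharge and 3 months also has no preparation stated. This is a fair reading, so 1.3 mL should not be treated as a fixed daily amount. But the number of preparations then needs to be written down.

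Third, the approved maximum can be looked up, and this is a single-centre study. That is correct: the cap can be checked, although not from the protocol alone. A reader might infer from 3.80 mL that the cap is at risk. The documents give no figure for it, so they show no breach.

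Fourth, section 2.0 expects only short ultrasound applications before intervention, and section 12 aims not to delay standard care. At the slower rates, session A may well be fully covered. This stands, and limits the claim about the primary outcome.

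Finally, section 11.1 says that procedural data will be collected. The form itself is not in the documents, so it cannot be said that infused volume goes unrecorded, only that it is not named.

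**Conclusion.** The inconsistency holds. One stated preparation covers 10.3 to 25.7 min, which is 4.35 to 19.74 min (14.5% to 65.8%) short of 30 min, before either day-1 diagnostic echo is counted. The result survives all four readings of the dilution. Its consequence is conditional: under Table 1, an unstated further preparation is needed; under the synopsis, exposure varies 2.5-fold and session B may be curtailed.

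It is tempting to conclude that the primary outcome is compromised. The documents do not show this, since the durations of the baseline echo and session A are missing; the main effect is on session B and the post-PCI secondary outcomes. This should be fixed, but it does not by itself invalidate the primary analysis.

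**What to change.** Reconcile the synopsis Treatment row, section 5.2 and Table 1 so that preparation volume, rate range, duration (maximum or required total) and number of day-1 preparations agree. The reconciled text should make clear which preparation serves the baseline echo, session A, session B and the post-intervention echo. State the cap on total agent as a figure that the sponsor takes from the approved labelling, and check the reconciled schedule against it.

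Record on the case report form the volume infused and the contrast-on minutes, separately for sessions A and B, and report both alongside the patency result.

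No dose, rate, duration or rule for counting treatment time is proposed here; those are for the sponsor to settle. The cost is a wording amendment and a few form fields.

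### Minor: the echo definition of spontaneous reperfusion (8.2.3) can count recovery produced by PCI; separately, the 15-beat loop is too short to show perfusion score 3 above 78 bpm

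*Combined protocol and SAP*

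**What the plan says.** **Definitions of spontaneous reperfusion (section 8.2).** The angiographic version (8.2.1) is TIMI 2-3 flow at the first contrast injection, before PCI. The ECG version (8.2.2) uses the tracing taken just before the angiogram. The echocardiographic version (8.2.3) accepts a score of 1 or 2 in the infarct segments, joined by an and/or to recovery of systolic function at follow-up. It does not say which score is meant or when it is read. A note at the end of 8.2.1 says that other definitions are collected but do not form the primary endpoint.

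**Echo schedule (Table 1 in section 5.2).** There are four diagnostic recordings: baseline, post-intervention, day 3/discharge and 3 months. The first treatment session, A, is to "start immediately after MCE", that is, after the baseline recording. Session B is to "start immediately after reperfusion to complete a total of 30 min".

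**Loop and scale (section 5.2).** The plan states "Loops of 15 cardiac cycles will be recorded using low mechanical index (MI) ultrasound". Each loop contains one high-MI impulse, "delivered after the second cardiac cycle of the loop". The microvascular perfusion score index (MPSI) is scored from the recordings. Score 1 is replenishment within 4 s. Next comes "a score of 2 (mildly reduced) when complete replenishment within the risk area is delayed longer than 4 s after the HMI impulse". Score 3 is "virtually no replenishment of myocardial contrast over 10 s after the MI impulse". No minimum loop time in seconds is given.

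**The concern.** The first and more important part is that 8.2.3 is not confined to the period before PCI. Every patient is expected to have primary PCI, and recovery of wall motion over the following days or months is what successful PCI may produce. A definition that lets such recovery qualify on its own cannot separate reperfusion before the procedure from reperfusion caused by it. If a rate is reported under this label, next to the angiographic and ECG rates, a reader will take all three as pre-PCI results.

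The second part is a mismatch between the recording rule and the scoring rule. The loop is fixed in beats and the score in seconds, so at faster heart rates the loop ends before the time that score 3 requires. A segment that is virtually empty when the loop stops, but would fill before 10 s, could be scored 3 when the scale calls for 2. MPSI is one of the five secondary outcomes in section 7.2.

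**Working it through.** **Part 1: definitions set against the schedule.** No arithmetic is needed.

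| Definition | Latest time allowed |
|---|---|
| 8.2.1 angiographic | first contrast injection, before PCI |
| 8.2.2 ECG | just before the angiogram |
| 8.2.3 echo, score | none stated |
| 8.2.3 echo, function | follow-up, so after PCI |

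Take a patient with an occluded artery at first injection and no ST resolution beforehand, whose artery is opened by PCI and whose wall motion has recovered by 3 months. Under 8.2.1 and 8.2.2 this is not spontaneous reperfusion. Under 8.2.3 it is. A perfusion score of 2 on the post-intervention echo would give the same result through the other limb.

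In Table 1, one of the four recordings precedes session A, three follow PCI, and none (0 of 4) lies between session A and PCI. Restricting 8.2.3 to pre-angiogram images therefore leaves only the baseline echo. That echo describes the patient before the treatment session and cannot show an effect of sonothrombolysis.

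**Part 2: loop time against the 10 s criterion.** The inputs from section 5.2 are 15 cycles, the flash after cycle 2, and boundaries at 4 s and 10 s. Heart rate (HR) is not in the documents, so the values below are assumed.

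- Beats after the flash: 15 − 2 = 13.
- Time after the flash: 13 × 60 / HR = 780/HR seconds.
- This falls below 10 s when HR > 780/10 = 78 bpm.
- It falls below 4 s only when HR > 780/4 = 195 bpm, so the boundary between scores 1 and 2 is not affected.
- If the flash takes half a beat or a whole beat, the 10 s limit falls to 12.5 × 6 = 75 bpm or 12 × 6 = 72 bpm.

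| HR (bpm) | Time seen (s) | Unseen before 10 s (s) |
|---|---|---|
| 78 | 10.0 | 0 |
| 80 | 9.75 | 0.25 |
| 90 | 8.67 | 1.33 |
| 100 | 7.80 | 2.20 |
| 120 | 6.50 | 3.50 |

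One segment moved from 2 to 3 raises a patient's MPSI by 1/17 = 0.06 if all 17 segments are scored, and by more if attenuated basal segments are left out. This is arithmetic for a single segment and not an estimate of a patient-level shift.

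**The case against.** **Little depends on 8.2.3.** It is not a listed secondary outcome, section 9 plans no analysis of it, and no objective or go/no-go rule uses it. That stands, and it is why the point is minor. But the data will be collected, and following the definition as written gives the wrong label.

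**The score limb could be read at baseline, which is before PCI.** True, but the text does not require it, and the function limb would still qualify alone.

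**The loop problem is only a possibility.** It needs a heart rate above 78 bpm, a segment virtually empty at loop end, filling in the short unseen gap, and a reader who assigns 3. A reader might instead leave the segment out, since the index divides by segments analysed. The plan also refers to a published imaging method that cannot be checked here. All of this stands, and it makes the second part an inexpensive improvement and not a demonstrated error.

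**Stronger readings that the documents do not support.**

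- A reader might infer that change in MPSI between visits is distorted because the window moves with heart rate. The only nearby wording is "The focus will be set at the mitral valve level for all studies", which concerns focus and not loop length. No heart rates are given at any visit.
- A reader might infer that treatment images from session A could rescue an echo rate. The plan says "The intervals between HMI impulses will vary from 5 to 15 s depending on the time required for myocardial contrast replenishment" and does not say that these images are saved. Filling could be seen at any interval, but score 3 could be supported only at 10 s or more. Patients without filling and with short intervals would drop out, so the rate would be selective.
- A reader might infer that the patency result is compromised. Neither the primary outcome nor the >60% criterion uses echo.

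**Conclusion.** The point holds, at minor severity.

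Section 8.2.3 is wrong as written: it permits reperfusion achieved by PCI to be called spontaneous, in conflict with the two definitions before it. This rests on the text and on Table 1 alone. The one assumption is that the unnamed score is the perfusion score. If it is, its cut falls between scores 2 and 3, the same boundary that the loop length affects.

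The loop mismatch is exact in arithmetic (780/HR seconds, limit 78 bpm) but unknown in consequence. Without heart rates or filling times, the number of segments involved cannot be stated. Only the boundary between scores 2 and 3 is exposed; segments already filling by loop end are scored correctly.

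**What to change.** **Section 8.2.3.** Delete the clause that admits functional recovery at follow-up. Name the score as the perfusion score. Restrict the definition to images acquired before the angiogram. Report post-PCI perfusion and functional recovery separately, under a name that does not include the word spontaneous. Then either state that a rate from the baseline echo describes patients before treatment and cannot show an effect of sonothrombolysis, or report no echocardiographic spontaneous reperfusion rate. This costs only a change of wording.

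**Section 5.2.** Define the diagnostic loops used for MPSI by time, at least 10 s after the flash. Treatment impulses are not touched. The extra low-MI recording is nil at or below 78 bpm and otherwise 10 − 780/HR seconds per loop:

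| Loops per study (assumed) | 90 bpm | 120 bpm |
|---|---|---|
| 3 (one in each of three views) | 3 × 1.33 = 4.0 s | 3 × 3.50 = 10.5 s |
| 9 (three in each of three views) | 9 × 1.33 = 12 s | 9 × 3.50 = 31.5 s |

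The documents do not fix the number of loops. Section 5.2 says that flash imaging is repeated in diagnostic practice and that the trial uses the same techniques, so the second row should be kept in view. For the baseline study this time falls before PCI, where section 12 asks that delay be avoided.
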